10.6. Health Damage Compensation

Subjects will receive compensation for any study-related health damage caused to them in compliance with "Compensation for Health Damage on Subjects" that is a separate document prepared by the Sponsor in each country or region. The Sponsor will purchase health insurance as an action for performance of liability for compensation and liability indemnity, as necessary.

10.7. Publication

If the entire results obtained from this study are to be disclosed (submission of paper/article, publication of book or presentation at professional meetings, etc.), the Development Sponsor will decide the authorship or presenter, based on the discussion with medical experts, in accordance with the Uniform Requirements for Manuscripts Submitted to Biomedical Journals (International Committee of Medical Journal Editors). A copy of any publication or written presentation of the data or script of any oral presentation of the data must be provided to the Development Sponsor for review and approval prior to submission for publication or presentation, including abstracts for professional meetings.

If any specific data on individual subject at each investigational site is to be published, the author or presenter will have discussion, in advance, with the Sponsor about the contents.

Appendix 1: ECOG Performance Status Scale

Score	Description
0	Fully active, able to carry on all pre-disease performance without restriction
1	Restricted in physically strenuous activity but ambulatory and able to carry out work of a light or sedentary nature, e.g., light house work, office work
2	Ambulatory and capable of all selfcare but unable to carry out any work activities; up and about more than 50% of waking hours
3	Capable of only limited selfcare; confined to bed or chair more than 50% of waking hours
4	Completely disabled; cannot carry on any selfcare; totally confined to bed or chair

Appendix 2: Pharmacy Guide

1. Packaging and Formulation

The investigational drug will be supplied as a sterile, white to off-white, lyophilized powder in glass vials containing 150 mg of darinaparsin per vial. Each vial and box will be labeled according to country- and region-specific regulations, and each box will have 10 vials of investigational drug. The label will comply with local regulations.

2. Labeling

A box and each vial of investigational drug will be properly labeled identifying the limited use to clinical study, name of the investigational drug, lot number, name and address of the sponsor, appropriate storage conditions, and appropriate country- and region-specific caution statement.

3. Storage and Expiry Date

The investigational drug should be stored under refrigeration at 2°C to 8°C (36°F to 46°F), except when being prepared for injection.

The expiry date of the investigational drug will be notified in writing by the Sponsor or CRO based on the results of stability studies that is being conducted concurrently with this study.

4. Calculation of Administration Dose

The dose (mg) of the investigational drug given to each subject will be calculated by multiplying the subject's body surface area (BSA, m²) by 300 (mg). The maximum dose will be 600 mg; a dose exceeding 600 mg per body must not be administered.

The BSA will be calculated using DuBois's formula shown below, based on the subject's height (cm) and body weight (kg) measured during the screening period.

$$S = W^{0.425} \times H^{0.725} \times 0.007184$$

S: Body surface area (m²)

W: Weight (kg)

H: Height (cm)

If there are ±10% changes in the body weights measured on Day 1 of each cycle (before the start of investigational drug administration) from the weight measured in the screening period, BSA will be re-calculated to adjust the dose.

5. Preparation

The preparation of investigational drugs will be performed at each investigational site by using aseptic techniques at room temperature.

Since SP-02L is a cytotoxic antitumor drug, handling of the drug should strictly comply with precautions as required for the handling of toxic chemicals. Protectors (goggles, gloves, masks, etc.) are required at the preparation. If the drug or drug solution attached to the skin,

the attached area should be washed well with soap and water immediately and if to the mucosa, rinsed well immediately. If the drug solution spills out, it should be wiped out with an absorbable material and the area should be cleaned with water and alcohol more than three times.

Each vial contains 150 mg of darinaparsin. When completely reconstituted with 2.0 mL water for injection, the nominal concentration is 75 mg/mL. Within 1 hour of reconstitution, the required dose (mg) is drawn into at least one syringe and added to an infusion bag containing 250 mL of saline solution (Sodium Chloride Injection).

In case that a lot number of investigational drug is multiple at the investigational site, the investigational drugs of the same lot number will be used in a subject throughout a cycle whenever possible; a subject will not receive the investigational drug of multiple lot numbers within a cycle.

6. Administration

The investigational drug will be reconstituted and diluted according to the preparation procedures described in above 5, and will be given intravenously over 1 hour (\pm 10 minutes) on each day of administration. After the infusion, a flushing with a sufficient amount of saline will be done to ensure all the drug remaining in the infusion route is infused fully to the subject.

Since the injection site abnormalities have been frequently reported in subjects who received the investigational drug via a peripheral line in the previous clinical studies, the administration of the investigational drug is recommended to be given through the central vein (e.g., via an implantable subcutaneous infusion port, a central venous catheter, a peripherally inserted central venous catheter). If any abnormal finding at the injection site is observed during the infusion via a peripheral line, the administration will be held at the discretion of the principal investigator or sub-investigator. Saline may be infused via a three-way stopcock. The IV infusion may be given from another peripheral vein or via a central venous line or port.

The following matters should be noted when the investigational drug is administered:

- During the injection via a peripheral line, full care should be taken to avoid extravasation. If any extravasation is observed, the dose will be held immediately, medical procedures will be provided for it, and a change in the peripheral vein for IV infusion will be considered.
- No other drug for injection should be given concurrently via the same IV line.
- The investigational drug administration will be started at the same time as much as possible in subjects for pharmacokinetic assessment in Cycle 1.

Destruction of Used Investigational Drugs

Used investigational drugs and boxes (empty boxes) will be destroyed locally in accordance with the investigational site's policy. The local destruction of used investigational drugs will be documented, as needed, according to the investigational site's policy. In case that the investigational site is incapable of local destruction of used investigational drugs and empty

boxes, the detailed procedures of destruction will be specified in the procedure manual of investigational drug management.

7. Supply and Return of Drug

After the conclusion of the clinical trial contract, the Sponsor will ship investigational drugs, via CRO or an investigational drug delivery service company, to the person in charge of the investigational drug management (e.g. pharmacist) at the investigational site. On receipt of the investigational drugs, the person in charge of the investigational drug management will conduct an inventory of the supplies and check condition of drugs. Also a “Proof of Receipt of Investigational Drug” should be completed and submitted to the Sponsor and a “Proof of Delivery of Investigational Drug” should be retained at the investigational site.

At the end of study, or as otherwise directed, the Sponsor will collect unused investigational drugs, via CRO or an investigational drug delivery service company. On return of unused investigational drugs, the person in charge of the investigational drug management will complete the check of amount and condition of unused drugs. A “Proof of Return of Investigational Drug” must be completed and submitted to the Sponsor, and a “Proof of Collection of Investigational Drug” should be retained at the investigational sites.

8. Investigational drug Accountability

The person in charge of the investigational drug management will prepare an “Investigational Product Accountability Record” including the following items and maintain it with updated information at all times.

- investigational drug substance code or product code
- receipt date and quantities, and expiry date of investigational drug
- lot number
- subject identification (subject number)
- dispensing log: date and quantity of dispensing and remaining quantity after subject dispensing
- information to identify the pharmacist who dispenses the investigational drugs
- date and quantity of investigational drug returned to the drug management unit, if appropriate
- record of destruction or loss of unused investigational drug
- record of destruction of used investigational drug (empty vial) as needed

12.2.4	Summary of ECG Parameters	16
12.2.5	Summary of PK Parameters	16
13	LISTING.....	17

Abbreviations and Terms

List of Abbreviations

Abbreviation	Definition
AE	Adverse Event
AESI	Adverse Event of Special Interest
AITL	Angioimmunoblastic T-cell Lymphoma
ALCL	Anaplastic Large Cell Lymphoma
BSA	Body Surface Area
CI	Confidence Interval
CR	Complete Response
DCR	Disease Control Rate
DOR	Duration of Response
ECG	Electrocardiogram
eCRF	electronic Case Report Form
FAS	Full Analysis Set
IPI	International Prognostic Index
NCI-CTCAE	National Cancer Institute Common Terminology Criteria for Adverse Events
ORR	Overall Response Rate
OS	Overall Survival
PFS	Progression-Free Survival
PIT	Prognostic Index for T-cell lymphoma
PD	Progressive Disease
PK	Pharmacokinetics
PKS	Pharmacokinetics Analysis Set
PPS	Per Protocol Set
PR	Partial Response
PTCL	Peripheral T-cell Lymphoma
PTCL-NOS	PTCL-not otherwise specified
RD	Relapsed Disease
SAF	Safety Analysis Set
SAP	Statistical Analysis Plan
SD	Standard Deviation
SD	Stable Disease
TTR	Time to Response

List of Terms

Term	Definition
SP-02	Drug substance code of Darinaparsin
SP-02L	Product code of Darinaparsin for injection
Day 1	The first day of 5 consecutive days of investigational drug administration in each cycle; including the case that the planned dosing on the first day is skipped
First screening visit	The day at which the subject signs the informed consent
Screening period	The period from the day of the first screening visit to the day before the first day of Cycle 1 (Day 1 of Cycle 1)
Treatment period	The period from the first day of Cycle 1 (Day 1 of Cycle 1) to the day before the first examination, observation and investigation scheduled during the follow-up period
Follow-up period	The period from the day of the first examination, observation and investigation scheduled during the follow-up period to the day of the last examination, observation and investigation scheduled during the follow-up period (including follow-up adverse event assessment)
Study period	Period consisting of screening period, treatment period and follow-up
Baseline	Results at the last time point of examination, observation and investigation before the start of the first administration of investigational drug in Cycle 1
Tumor response	“Complete Response (CR)” and “Partial Response (PR)”
Overall Response Rate	Proportion of subjects with “CR or PR” in the evaluable subject population
Disease Control Rate	Proportion of subjects with “CR, PR or Stable Disease (SD)” in the evaluable subject population
Progression-Free Survival (PFS)	Time from the first day of investigational drug administration (Day 1 of Cycle 1) to the date of documented "progressive disease" or "relapsed disease", or the date of "death", which occurs earlier
Overall Survival (OS)	Time from the first day of investigational drug administration (Day 1 of Cycle 1) to the date of "death" from any cause
Time to Response (TTR)	Time from the first day of investigational drug administration (Day 1 of Cycle 1) to the first day of tumor response observed for patients who achieved a CR or PR
Duration of Response (DOR)	Time from the first day of tumor response observed for patients who achieved a CR or PR to the date of documented "progressive disease" or "relapsed disease", or the date of "death" which occurs earlier

1 OVERVIEW

This Statistical Analysis Plan (SAP) specifies details of the statistical analyses to be conducted for the clinical study titled “Asian Multinational Phase 2 Study of SP-02L (darinaparsin for injection) in Patients with Relapsed or Refractory Peripheral T-cell Lymphoma (PTCL)” (hereafter referred as to “this study”).

The purpose of the SAP is to describe general or study-specific statistical methodology for this study. Statistical results to be reported as an interim report or a final clinical study report (CSR). The SAP would be revised when the protocol is revised. It would also be revised if the revision is judged to make the data more credible and useful in comparison with the original plan.

2 STUDY OBJECTIVES

Primary objective

To evaluate the efficacy of SP-02L monotherapy in patients with relapsed or refractory PTCL

Secondary objectives

- To evaluate the safety of SP-02L monotherapy in patients with relapsed or refractory PTCL
- To assess the pharmacokinetic (PK) profile of SP-02L at multiple doses in a subgroup of subjects (cf. Section 2.6 of protocol)

3 STUDY DESIGN

This study is a phase 2 multinational, multicenter, single-arm, open-label, non-randomized study conducted in East Asia countries/regions. Subjects will receive SP-02L at 300 mg/m² once daily for 5 consecutive days followed by 16 days of rest per cycle of 21 day (3 week). SP-02L will be administered for 6 cycles to evaluate the efficacy and safety of SP-02L monotherapy using various endpoints. If the subject wishes to continue investigational drug administration and the investigator judges that the continuous administration of investigational drug is possible and necessary for the subject, the investigational drug administration can be continued beyond 6 cycles.

Pharmacokinetics will be assessed in subjects enrolled in part or all of the investigational sites in each participating country or region at Cycle 1.

4 END POINT

Primary Endpoint

Tumor response (best overall response) according to the Revised Response Criteria for Malignant Lymphoma by an International Working Group to Standardize Response Criteria for Non-Hodgkin's Lymphomas in 2007 (the best overall response up to Cycle 6 based on a central assessment by Efficacy and Safety Review Committee)

Secondary Endpoints

- Progression-Free Survival (PFS)

- Time to Response (TTR)
- Duration of Response (DOR)
- Overall Survival (OS)
- Occurrence of adverse events (AEs)
- SP-02L plasma concentration-time profile, PK parameters, and fraction of dose excreted in urine

5 ANALYSIS SETS

5.1 Efficacy Analysis Set

The “full analysis set (FAS)” will consist of subjects who fulfill eligibility criteria (cf. Section 3 of protocol) and who take a tumor response assessment (cf. Section 6.14.2 of protocol) at least one time after the administration of investigational drug. A group of subjects who have no important protocol deviation including violation of eligibility criteria and/or dosage and administration that may affect the efficacy evaluation is defined as “per protocol set (PPS)”. FAS will be used for the primary analysis of efficacy endpoints, and PPS will be used for the secondary analysis of efficacy endpoints.

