4.4.3. Procedures for Study Withdrawal

In a subject who is withdrawn from the study before the first dosing of investigational drug, the subsequent examination, observation and investigation are not required to be performed.

In a subject who is withdrawn from the study after the start of investigational drug administration and cannot continue any of the subsequent examination, observation and investigation; as cases such as the subject is not willing to provide any own clinical data after the withdrawal of consent or the subjects is pregnant at a possible risk from protocol-specified examination, the principal investigator or sub-investigator will take the best measures to stop the study in the subject, under the condition where the subject’s safety is ensured. In case of subjects have ongoing AEs, the best measures to follow the ongoing AEs should be carried out where possible.

In a subject who is withdrawn from the study after the start of investigational drug administration; on the condition that the subject still has a willing to provide own clinical data, the subsequent examination, observation and investigation scheduled during the current cycle and the follow-up period should be completed.

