5.5.2. Proscribed Therapy

Throughout the study, from the day of obtaining the informed consent to the end of follow-up period, none of the medications or treatments listed below should be proscribed for any reason. In any case a subject starts any of the medications or treatments for justifiable reasons, the subject will discontinue the study with the completion of examination, observation and investigation specified in the current cycle and the follow-up period:

- Anticancer chemotherapy other than the investigational drug, and anticancer immunotherapy

Continuous oral administration or injection of corticosteroid: equivalent to more than 10 mg/day of prednisolone, is also prohibited. However, single use or use as needed is allowed for the purpose including the treatment for fever or pretreatment for blood transfusion.

- Radiotherapy
- Hematopoietic stem cell transplants
- Cellular immunotherapy (e.g., cancer vaccine therapy)
- Gene therapy
- Major surgery; e.g., surgery with general anesthesia, craniotomy/thoracotomy /laparotomy)
- Any other investigational drugs, therapeutic drugs that are not approved by each country or region; excluding drugs which are already approved for off-label use, and investigational devices

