6.14.2. Tumor Response Assessment

At the following time points, the clinical assessments and radiological assessments will be performed by the same examinations and imaging tests under the same procedures and conditions at baseline assessment, and the tumor responses will be assessed throughout the study. Any site of new lesion will be identified. Bone marrow assessment (biopsy or aspiration) will be required only if bone marrow is positive at baseline and the radiographic responses is judged to be CR.

- Any day between Day 15 and Day 21 in Cycle 3
- Any day between Day 15 and Day 21 in Cycle 6
- If administration of investigational drug is continued beyond 6 cycles, any day between Day 15 and Day 21 every 3 (\pm 1) cycles from Cycle 7
- If administration of investigational drug is discontinued at a cycle other than the above, any day between Day 15 and Day 42 in the last cycle; however, before the initiation of the subsequent treatment of primary disease

According to the response criteria defined in Table 7, the local assessment of tumor response will be performed by the principal investigator or sub-investigator.

Table 7: Revised Response Criteria for Malignant Lymphoma by an International Working Group to Standardize Response Criteria for Non-Hodgkin's Lymphomas in 2007

Response	Definition	Nodal Masses	Spleen, Liver	Bone Marrow
CR	Disappearance of all evidence of disease	(a) FDG-avid or PET positive prior to therapy; mass of any size permitted if PET negative (b) Variably FDG-avid or PET negative; regression to normal size on CT	Not palpable, nodules disappeared	Infiltrate cleared on repeat biopsy; if indeterminate by morphology, immunohistochemistry should be negative
PR	Regression of measurable disease and no new sites	\geq 50% decrease in SPD of up to 6 largest dominant masses; no increase in size of other nodes (a) FDG-avid or PET positive prior to therapy; one or more PET positive at previously involved site (b) Variably FDG-avid or PET negative; regression on CT	\geq 50% decrease in SPD of nodules (for single nodule in greatest transverse diameter); no increase in size of liver or spleen	Irrelevant if positive prior to therapy; cell type should be specified
SD	Failure to attain CR/PR or PD	(a) FDG-avid or PET positive prior to therapy; PET positive at prior sites of disease and no new sites on CT or PET (b) Variably FDG-avid or PET negative; no change in size of previous lesions on CT		

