6.14.3. Radiological Assessment at the Central Imaging Review Institution

The principal investigator or sub-investigator (or designated staff) will submit imaging data by CT and FDG-PET at the following time points to the Central Imaging Review Institution. Details of the procedures of imaging data submission to the Central Imaging Review Institution are specified in a separate document.

- Screening period (between Day -28 and Day -1)

- Any day between Day 15 and Day 21 in Cycle 3
- Any day between Day 15 and Day 21 in Cycle 6
- If the administration of investigational drug is discontinued at Cycles 1, 2, 4 and 5, any day between Day 15 and Day 42 in the last cycle; however, before the initiation of the subsequent treatment of primary disease

The Central Imaging Review Institution will measure the tumor size of lymphoma lesions and evaluate FDG accumulation; according to the predefined procedure, and submit the radiological assessment results to the Efficacy and Safety Review Committee.

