6.15. Survival Surveillance

6.15.1. Surveillance of Progression of Disease and Relapsed Disease

If PD, RD or “death” is not confirmed by the end of follow-up period, tumor response assessment [See Section 6.14.2] will be continued at intervals of three months or less until PD, RD or “death” is confirmed.

PD or RD includes not only the results of the radiological assessment with imaging data but also “symptomatic progression” at the principal investigator’s or sub-investigator’s judgement based on clinical symptoms or laboratory findings, etc. The development of secondary cancer is not defined as progression event, and surveillance of PD, RD or “death” will be continued.

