9.1.2. Efficacy Analysis Set

A subject group consisting of subjects who fulfill eligibility criteria [See Section 3.1] and who take a tumor response assessment [See Section 6.14.2] at least one time after the administration of the investigational drug is defined as a "Full Analysis Set (FAS)". A subject group consisting of subjects who have no important protocol deviation including violation of eligibility criteria and/or dose and dosage that may affect the efficacy evaluation is defined as "Per Protocol Set (PPS)". FAS will be used for the primary analysis of efficacy endpoints, and PPS will be used for the secondary analysis of efficacy endpoints.

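### The primary efficacy set leaves out eligible treated subjects with no post-dose tumour assessment, and no rule counts them as non-responders, so the ORR can only be equal or higher than if they were counted

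*SAP*

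**What the plan says.** The SAP (5.1) admits to the FAS eligible subjects "who take a tumor response assessment (cf. Section 6.14.2 of protocol) at least one time after the administration of investigational drug". Protocol 9.1.2 has the same condition: "who take a tumor response assessment [See Section 6.14.2] at least one time after the administration of the investigational drug". Both make the FAS primary for the efficacy endpoints and the PPS secondary.

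ORR is the share of CR or PR in an evaluable population that is not defined further (Protocol Study Glossary; SAP List of Terms). Protocol 9.4 imputes nothing. SAP 8.2.2 disregards withdrawal and completes only missing birth dates. SAP 5.2 gives the safety set no role in efficacy. SAP 11.1 to 11.4 plans no ORR on all treated subjects.

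Several provisions keep the number of unassessed subjects down:

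- Protocol 6.14.2 asks for a scan after early discontinuation on "any day between Day 15 and Day 42 in the last cycle; however, before the initiation of the subsequent treatment of primary disease".
- Protocol 6.14.3 sends such scans to central review: "If the administration of investigational drug is discontinued at Cycles 1, 2, 4 and 5".
- For withdrawn subjects still willing to give data, Protocol 4.4.3 says that "the subsequent examination, observation and investigation scheduled during the current cycle and the follow-up period should be completed".
- For those who start a proscribed therapy, Protocol 5.5.2 says that "the subject will discontinue the study with the completion of examination, observation and investigation specified in the current cycle and the follow-up period".
- Protocol 6.15.1 continues tumour assessment after follow-up: it "will be continued at intervals of three months or less until PD, RD or" death is confirmed.

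**The concern.** Entry to the primary set depends on something that happens after dosing. Three groups of eligible treated subjects can still fail to enter:

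- those who die before a first scan;
- those who refuse to provide further data (Protocol 4.4.3);
- those stopped for symptomatic progression without imaging (Protocol 5.4.3, criterion 2) who then miss the stopping scan. Protocol 6.15.1 treats that judgement as progression ("PD or RD includes not only the results of the radiological assessment with imaging data but also" symptomatic progression), so no later scan is required. No text says whether the judgement is itself a tumour response assessment for FAS entry.

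None of these subjects can be recorded as CR or PR. The trial has one arm and is judged against a fixed 10%, so no comparator shares the bias. The allowance from 55 to 65 subjects in Protocol 9.2 is for central-pathology exclusions only. Open enrolment until 65 subjects have had at least one cycle (Protocol 4.5) protects the numbers, not the denominator.

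PFS and OS use the same set. Both are defined to count death, yet an observed death before any scan drops out of both analyses.

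**Working it through.** **Inputs.** Threshold 10%, expected ORR 25%, one-sided 5%, power 90%, required n 55, planned n 65 (Protocol 9.2). Binomial test against 0.10 (SAP 11.1). 90% Clopper-Pearson interval (SAP 8.1.1 and 11.1). SAP 8.1.1 also says that no tests will be performed, but requiring the lower bound of that interval to exceed 10% gives the same decision. The share unassessed is not given, so 5%, 10% and 15% are assumptions.

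**1. The plan's own figure.** Let c(n) be the smallest count with P(X ≥ c | n, 0.10) ≤ 0.05. The smallest n with power of at least 90% at 25% is 55, with c = 10, error 4.44% and power 91.1%. This reproduces the plan. Cut-offs: 9 for n = 42-48, 10 for 49-56, 11 for 57-63, 12 for 64-71.

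**2. When the first scan falls.** On treatment it is due on Day 15-21 of Cycle 3, nominally Day 42+15 = 57 to 42+21 = 63. Two cycle intervals of -1 to +7 days (Protocol 5.3.1) widen this to Day 55-77. The 3-week postponement for a related AE (Protocol 5.4.3, criterion 5) can make it later.

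**3. Effect on the estimate.** With x responders among N eligible treated subjects, m of them unassessed, the FAS gives x/(N-m) and the alternative gives x/N. The ratio is 1/(1-s) with s = m/N: 1/0.95 = 1.05, 1/0.90 = 1.11, 1/0.85 = 1.18. The two are equal if m = 0 or x = 0.

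**4. Effect on the error rate, if 10% is the true ORR among all eligible treated subjects.** Assume that each subject is unassessed independently with probability s and that none of the unassessed responds. The rate among those assessed is then 0.10/(1-s), and

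error = Σ over m of P(m | N, s) × P(X ≥ c(N-m) | N-m, 0.10/(1-s)).

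| N | s = 0 | 5% | 10% | 15% |
|---|---|---|---|---|
| 55 | 4.4% | 4.5% | 5.7% | 7.9% |
| 60 | 3.4% | 4.6% | 6.7% | 8.1% |
| 65 | 2.6% | 5.1% | 6.5% | 8.9% |

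If the 10% describes assessed subjects only, the rate among them is 0.10 and the level holds.

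**5. With m fixed.** Error = P(X ≥ c(N-m) | N-m, 0.10N/(N-m)). At N = 55 the cut-off stays at 10 for m = 0 to 6 (n = 55 down to 49), and the error stays at 4.3-4.4%. At m = 7 the cut-off falls to 9 and the error is 9.3%.

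**6. A result near a cut-off.** 11/65 = 16.9%, p = 0.057, lower bound 9.8%: not above the threshold. With two of the 65 unassessed and left out, 11/63 = 17.5%, p = 0.047, lower bound 10.1%: above it.

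**The case against.** The strongest reply is that this is a pre-specified response-evaluable set in a single-arm phase 2 trial, that losses are limited by a required stopping scan, and that a 5% loss leaves the error essentially nominal (4.5-5.1%). The planned counts of treated subjects, safety set and FAS, with reasons for withdrawal (SAP 10.1.1 to 10.1.3), will also make the gap visible. All of this stands. It limits the size and the severity, but it puts no excluded subject back into the denominator.

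Four stronger readings are tempting, and the documents do not support them.

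- *One unassessed subject breaks the 5% level.* At N = 57 and N = 64 the fixed-m error does pass 5% at m = 1 (5.5% and 5.1%). There the cut-off also drops by one from a test that ran at only 2.4%, so bias is mixed with discreteness.
- *FAS members without a central response have no rule.* ORR is the share with CR or PR, and the FAS is the primary set. On the plain reading, a FAS member without a central CR or PR is already a non-responder. The gap concerns subjects outside the FAS.
- *Earlier studies give the expected loss.* Protocol 1.3.1 reports 5 of 7 PTCL subjects evaluable in one study. It also reports an efficacy set of 14, from 23 treated, in the phase 1 studies. The phase 1 set also required two cycles, and reasons for exclusion are not given, so neither ratio estimates the share under this rule.
- *The 5% level is certainly exceeded.* That depends on which population the 10% describes, and the documents do not say.

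**Conclusion.** The point holds and should be fixed. The direction is certain relative to counting the unassessed as non-responders. It is not a statement about what ORR would have been had everyone been scanned.

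The size is unknown because m is unknown. Under the assumed shares, ORR is inflated by a factor of 1.05 to 1.18. The error rate is near nominal at 5% unassessed and reaches 7.9-8.9% at 15%, but only if the threshold refers to all eligible treated subjects and the unassessed do not respond. Near a cut-off, two subjects can change the conclusion. Further from it, as with up to six at N = 55, the test cut-off does not move although the estimate still rises.

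PFS and OS are expected to look longer because early deaths are dropped. That is not certain: if the excluded are mainly people who refused further data and lived longer than the rest, the sign reverses.

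**What to change.** Define the primary efficacy set as all eligible subjects, including a centrally confirmed eligible subtype, who received at least one dose. In the primary ORR, count those with no central response assessment up to Cycle 6 as non-responders. Analyse PFS and OS on the same set, with death as an event and, for PFS, symptomatic progression as well. Censor PFS at Day 1 of Cycle 1 for subjects with neither an assessment nor an event. Keep the present FAS as a sensitivity analysis, and report the number unassessed with reasons. State which population the 10% threshold describes.

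The cost is protocol and SAP wording, with no new data, and a somewhat lower ORR. Changing the primary set in an open-label study under way is itself a pre-specification risk. Recording the change in SAP 7.4 before the data are fixed, and reporting both sets, limits it.

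Power should be restated. If 25% holds only among assessed subjects (assumption), power = P(X ≥ c(N) | N, 0.25(1-s)). Over N = 55 to 65 this is 87.6-94.2% with none unassessed, 82.7-91.1% at 5%, 76.5-86.8% at 10% and 69.1-81.1% at 15%. The ranges are wide because the cut-off steps with N. Restating these figures is enough; the point does not call for enrolling more subjects.
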